15.1.2 Statistical analysis plan and statistical method

Mortality at 1 year post-procedure, the primary endpoint, will be analyzed in the AT analysis set to verify the non-inferiority of EWJ-003 therapy to the standard therapy. The non-inferiority test will be performed

- 104 -

made and reasons for the changes, and the Statistical Analysis Plan should be revised.

All deviations from the Statistical Analysis Plan should be described in the Study Report.

- 106 -

using one-sided Fisher's exact test, and at one-sided significant level of 0.05 if the 95% CI upper limit for the mortality at 1 year post-procedure is lower than the PG (45%), non-inferiority of EWJ-003 therapy to the standard therapy would be verified.

No statistical tests will be conducted for the secondary endpoints, but evaluate by descriptive statistics. The secondary valve performance endpoints based on the echocardiographic evaluation will be analyzed in the VI analysis set, and other secondary endpoints. Other data including subject background and baseline characteristics, and procedure information, etc. will be summarized by descriptive statistics.

All statistical analyses will be performed for, in addition to the entire analysis sets, each approach of TF, TA, and TAO. For continuous variables, the number of measurements, mean, standard deviation, median, quartile, minimum, maximum, and 95% CI of the mean will be calculated. On the other hand, for categorical variables, the number of samples (n), percentage (%), and for binary variables 95% CI will be calculated. For the primary endpoint and secondary safety and efficacy endpoints, the cumulative incidence will be calculated by Kaplan-Meier estimates as needed.

The detailed statistical analysis plan and statistical method are included in the Statistical Analysis Plan.

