As for reports in Japan, Ohno et al. reported that 26 Japanese AS patients who received drug therapy (including 2 dialysis patients) showed the mortality at 1 year post-treatment of 53.1%^[35]. That was nearly consistent with the above-mentioned PARTNER-US study results, and the mortality at 1 year post-drug therapy in Japanese non-dialysis patients was estimated as approximately 50%. Ohara et al. reported that 12 out of 16 Japanese chronic dialysis AS patients (75%) died during mean follow-up period of 32 ± 17 months,^[10] and considering that among 16 patients only 2 patients received sAVR, the mortality in 14 patients who received drug therapy may be at least 71.4% (10/14). This was similar to 3-year mortality (70.7%) in 26 AS patients (including 2 dialysis patients) reported by Ohno et al., but the mean age of patients 68 ± 10 years was significantly lower than that reported by Ohno et al. (mean age 84.1 ± 5.3 years). In addition, considering that the mean patient age in the advanced medical care given at Osaka University Hospital was 76.7 ± 5.1 years, the prognosis in the drug therapy group assumed for this clinical trial can be predicted as poorer than that reported by Ohara et al., and the 1-year mortality may be over 50%.

- 45 -

the predicted mortality at 1 year post-procedure (true value) in this clinical trial was set as 20%. As previously mentioned, the PG was set as 45%, and the number of subjects required to reject the null hypothesis (H₀: Mortality at 1 year post-procedure is ≥ 45%) with one-sided α = 0.05 was calculated as 24 subjects. A sample size of 24 subjects will provide 81.1% power by one-sided Fisher's exact test. To account for the drop-out, a total of 30 subjects was determined for the target sample size for this trial. The sample size was computed using PASS 11 software.

- PG = 45%
- Predicted mortality at 1 year post-procedure (true value) = 20%
- H₀: Mortality at 1 year post-procedure ≥ 45%
- H_A: Mortality at 1 year post-procedure < 45%
- One-sided Fisher's exact test.
- Level of significance α = 0.05

Rationale for the setting of predicted mortality at 1 year post-procedure (true value)

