15.1.1.2 As-treated analysis set

A subject population consisting of subjects who were enrolled in this clinical trial and implantation of the study device was initiated is defined as as-treated (AT) analysis set. The time when invasion such as incision was made on the access site is regarded as the start of the study procedure. The primary endpoint and secondary safety and efficacy endpoints will be analyzed in the AT analysis set.

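### The primary test treats 1-year mortality as a simple proportion and states no rule for AT subjects with unknown day-365 status; either obvious handling distorts it, and a Kaplan-Meier limit would not

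*Combined protocol and SAP*

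**What the plan says.** - **Test and set.** Section 15.1.2: "Mortality at 1 year post-procedure, the primary endpoint, will be analyzed in the AT analysis set". The test is a one-sided Fisher's exact test "at one-sided significant level of 0.05", and success is an upper 95% confidence limit below the 45% performance goal. Whether that limit is one- or two-sided is not stated.
- **Who is in the set.** Section 15.1.1.2 defines it as "A subject population consisting of subjects who were enrolled in this clinical trial and implantation of the study device was initiated". Completed follow-up is not required.
- **Sample size.** Section 4.3, rationale: "A sample size of 24 subjects will provide 81.1% power by one-sided Fisher's exact test", and then "To account for the drop-out, a total of 30 subjects was determined for the target sample size for this trial". The same section says that discontinued subjects are not replaced.
- **Kaplan-Meier.** Section 15.1.2 adds that "the cumulative incidence will be calculated by Kaplan-Meier estimates as needed". This is not tied to the success criterion.
- **Follow-up.** Section 7.3 ends required follow-up for subjects who leave the procedure without the study valve, although they remain in the AT set. Sections 10.2.9 and 14.2 ask for safety follow-up after discontinuation as far as possible, and 14.3 asks for contact after a missed visit, including confirmation of survival.
- **Further detail.** Section 15.1.2 defers it to a separate Statistical Analysis Plan.

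**The concern.** An exact test of a proportion needs each subject classed as dead or alive at one year. It has no place for a subject last known alive at, say, month five. The plan expects losses, does not replace them, and creates one group with no required follow-up from day 0, yet it does not say how such subjects enter the test.

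Two simple conventions are available, and each biases the estimate even when loss is unrelated to risk. Keeping them as survivors lowers the apparent mortality, because deaths after loss are not seen. Removing them raises it, because a subject who dies before the moment of loss is kept while one lost alive is not. This is the trial's only hypothesis test, and by section 18.3 the 1-year report supports the approval application. The choice should not be open once the data are known.

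**Working it through.** **Inputs.** From sections 4.2.1, 4.3 and 15.1.2: goal 45%, assumed true mortality 20%, one-sided alpha 0.05, 24 subjects raised to 30. Derived: 30 − 24 = 6, and 6/30 = 20%. Assumed, not in the documents: constant death hazard, loss independent of death, and the loss rates and times shown below.

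**1. The plan's own figure.** With one sample and a fixed goal, the test is the exact binomial. For n = 24 the boundary is 6 deaths: P(X ≤ 6 | 24, 0.45) = 3.64% and P(X ≤ 6 | 24, 0.20) = 81.1%. The stated power reproduces.

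**2. Thirty subjects, complete follow-up.**
- One-sided 95% limit: boundary 8 (exact upper limit at 8/30 is 43.0%), false success 3.12%, power 87.1%.
- Two-sided 95% limit: at 8/30 the upper limit is 45.9%, so the boundary is 7, with false success 1.21% and power 76.1%.

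**3. Unknown status kept as survivor, random loss.** Let λ = −ln(1 − mortality) and δ = −ln(1 − loss). The proportion seen to die is λ/(λ+δ) × (1 − e^−(λ+δ)). At 45% mortality and 20% loss, λ = 0.5978 and δ = 0.2231, giving 0.7282 × 0.56 = 0.408. False success is then P(X ≤ 8 | 30, 0.408).

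| Loss by 1 year | Apparent mortality | False success, boundary 8 | Boundary 7 |
|---|---|---|---|
| 0% | 45.0% | 3.1% | 1.2% |
| 5% | 44.0% | 4.0% | 1.6% |
| 10% | 42.9% | 5.1% | 2.1% |
| 20% | 40.8% | 8.0% | 3.6% |

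**4. Same convention, exactly six losses.** Deaths seen are Binomial(24, 0.45) + Binomial(6, 1 − 0.55^t), with t the time of loss in years.

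| Time of loss | Boundary 8 | Boundary 7 |
|---|---|---|
| Day 0 | 17.3% | 8.6% |
| 3 months | 11.1% | 5.2% |
| 6 months | 7.2% | 3.1% |
| 9 months | 4.7% | 1.9% |

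With boundary 8 and mid-year loss of one, two, three or four subjects, the rate is 3.6%, 4.2%, 4.8% or 5.5%.

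**5. Unknown status removed, 20% random loss.**
- True 20%: λ = δ, so deaths seen are 0.5 × (1 − 0.64) = 0.18 and subjects followed alive to one year are 0.64. Apparent mortality is 0.18/0.82 = 22.0%.
- True 45%: 0.408/(0.408 + 0.440) = 48.1%.
- The number retained is Binomial(30, 0.82) or Binomial(30, 0.848) respectively. Averaging the one-sided exact rule over it gives power 71.6% and false success 1.6%.

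**6. Kaplan-Meier with a log-log limit.** The upper limit is 1 − S^exp(1.645 × √g/|ln S|), where g is the Greenwood sum. With no loss, S = 1 − k/30 and g = k/[30(30 − k)].
- k = 8: S = 0.733, g = 0.01212, limit 42.7% (success).
- k = 9: S = 0.700, g = 0.01429, limit 46.1% (no success).

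So with complete follow-up the decision is the same as 8 or fewer of 30: 3.12% false success and 87.1% power. Under loss, simulation gave 3.6% false success for six losses (uniform over the year or at mid-year; 20,000 runs) and 3.8% for random 20% loss (40,000 runs). Power was about 84% in each case. A plain Greenwood limit instead of log-log gave about 6.3% false success with six losses, so the type of limit has to be named.

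**The case against.** A reader might infer that the plan counts drop-outs as survivors and that its false-success rate is therefore 8%. The documents do not support that. Section 15.1.1.2 says who is in the set, not how unknown status is scored. Raising 24 to 30 reads at least as naturally as expecting about 24 evaluable subjects with the rest removed, and on that reading the error is conservative.

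Other limits also stand:

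- Neither six losses nor 20% is stated as a drop-out rate; both are back-calculated.
- Some drop-outs may leave before incision and never enter the AT set. Leaving the visit schedule is not the same as unknown survival, because sections 10.2.9, 14.2 and 14.3 ask sites to keep tracing subjects.
- With three or fewer mid-year losses the rate stays below 5% even if all are scored as survivors.
- If the confidence limit is two-sided, 20% random loss gives only 3.6%.
- The separate Statistical Analysis Plan is not in the text available and may contain a rule.

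These points limit the size of the effect; none supplies a rule in the text available. The removal reading does not rescue the design either, since it loses about ten points of the stated power. Nor should one claim that every figure behind the goal is Kaplan-Meier: section 4.2.1 also uses a crude annual death rate and relative risks. The 1-year rates in Tables 4-2 and 4-8 are, however, Kaplan-Meier based.

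**Conclusion.** The concern holds in conditional form. The plan tests a proportion in a set that can contain subjects of unknown 1-year status, and the available text does not say how they count. With a one-sided limit and unknowns kept as survivors, false success goes from 3.1% to about 8% under 20% random loss. It passes 5% at about 10% loss, and for six losses it ranges from 4.7% (9 months) to 17.3% (day 0). With a two-sided limit the 20% figure is about 3.6%. With unknowns removed, false success is about 1.6%, but power at 20% mortality is 71.6%.

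All of this assumes that lost subjects share the hazard of the others and that their status is not recovered. It does not show that the trial's error rate is in fact above 5%. It shows that the result depends on a convention left open, and that a method better than either convention is available. The change should be made, though the actual effect may be small if tracing is good.

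**What to change.** In section 15.1.2, make the primary decision: success if the one-sided 95% upper limit (log-log transformation, Greenwood variance) of Kaplan-Meier mortality at day 365 in the AT set is below 45%, with subjects of unknown status censored when last known alive. Naming the limit as one-sided also settles the boundary question. Report the exact binomial result as supportive, together with a bound that counts every subject of unknown status as dead. The latter is a bound only: with six unknowns at day 0, success needs 2 or fewer deaths among the other 24, which has a probability of 11.5% at 20% mortality.

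The cost is analysis wording; if the separate Statistical Analysis Plan already has a rule, align the two. Two drawbacks remain. The limit is asymptotic at n = 30, although the simulated error stays below 5%. Power is about 3 points lower than with complete follow-up (84% against 87.1%) if 20% are lost. Kaplan-Meier also assumes that loss is unrelated to risk, which is doubtful for subjects who leave the procedure without the study valve, and that is why the bound is needed.

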	
  
 Target sample size by approach	Target sample size	A total of 30 subjects	
   
 Transfemoral	≥ 2 subjects	
 
 Transapical	≥ 2 subjects	
 
 Transaortic	≥ 2 subjects	
 
 Target sample size by valve size		
 
 20 mm	≥ 1 subject	
 
 23 mm	≥ 1 subject	
 
 26 mm	≥ 1 subject	
 
 29 mm	≥ 1 subject	
  
	Target sample size by approach	Target sample size	A total of 30 subjects	Transfemoral	≥ 2 subjects	Transapical	≥ 2 subjects	Transaortic	≥ 2 subjects	Target sample size by valve size		20 mm	≥ 1 subject	23 mm	≥ 1 subject	26 mm	≥ 1 subject	29 mm	≥ 1 subject
Target sample size by approach	Target sample size	A total of 30 subjects																		
Transfemoral	≥ 2 subjects																			
Transapical	≥ 2 subjects																			
Transaortic	≥ 2 subjects																			
Target sample size by valve size																				
20 mm	≥ 1 subject																			
23 mm	≥ 1 subject																			
26 mm	≥ 1 subject																			
29 mm	≥ 1 subject																			
Sample Size Calculation	
The sample size for this trial was calculated based on the number of subjects required to verify noninferiority of the study treatment to the standard therapy by comparing the primary endpoint of all-cause mortality at 1 year post-procedure with the performance goal (PG). With the predicted mortality (true value) at 1 year post-procedure of 20% and PG of 45%, the number of subjects required to reject the null hypothesis (H_0: Mortality at 1 year post-procedure is $\geq 45\%$) with one-sided alpha of 0.05 was calculated as 24 subjects. A sample size of 24 subjects will provide 81.1% power by one-sided Fisher's exact test. To account for the drop-out, a total of 30 subjects was determined for the target sample size for this trial.
																			

Item	Content

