4.2 Performance Goal

4.2.1 Rationales for the performance goal setting

The PG was established by estimating mortality at 1 year post-procedure from the clinical research results of sAVR in chronic dialysis patients in Japan.

In the dialysis treatment between Japan and Europe and the US, there are some differences in physique of the patients, formulation of dialysis volume and duration of dialysis, patient control, and treatment compliance, and it is generally known that prognosis is better in Japan relative to Europe and the US. According to a large-scale global observation epidemiologic cohort research on medical care process and outcome of patients on maintenance dialysis (Dialysis Outcomes and Practice Patterns Study [DOPPS]), when the relative death risk adjusted for age, gender, race, and 15 concomitant diseases in Japan is assumed to be 1, it was 3.78 in the US, and 2.84 in Europe^[31]. Compared with non-dialysis patients, chronic dialysis patients have poorer prognosis after sAVR; it has been reported that the survival rate at 1 year post-procedure in the US was approximately 60%, at 3 years post-procedure approximately 40%, and at 5 years post-procedure approximately 30%^[9, 13] whereas in Japan good long-term results have been reported; at 1 year post-procedure 75% to 90%, at 3 years post-procedure 40% to 80%, and at 5 years post-procedure 30% to 60%^[14, 17, 32-33]. Therefore, upon estimating the mortality at 1 year post-procedure in chronic

- 40 -

dialysis patients underwent sAVR, the impact of the difference in the medical environment for dialysis between Japan and Europe and the US cannot be ignored, and thus the mortality at 1 year post-procedure was estimated based on the results of Japanese clinical research.

As shown in Table 4-1, there was no difference in the results of sAVR in chronic dialysis patients by type of artificial valve (bioprosthetic or mechanical valve)^[17, 32] for the setting of PG, regardless of bioprosthetic or mechanical, the results of both valves were used.

Table 4-1: Comparison of sAVR results in chronic dialysis patients by type of prosthetic valve

Author (year of publication/country)	Valve position	Implantation valve	Treatment results			Structural valve deterioration	
			30-day mortality	5-year survival rate ^{†3}			
K. Tanaka, et al ^[32] (2009/Japan)	Aortic valve	Bioprosthetic valve (N=22)	1/22 (4.5%) ^{†1}	---	55.7 ± 7.6%	p < 0.001 ^{†4}	0 subjects (FU: 42 ± 31 m)

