9.2.2 Secondary efficacy endpoints

- Device success: 30 days after procedure
- Length of post-procedural hospitalization/ICU stay: At discharge
- NYHA classification: Post-procedure 30 days, 6 months, 1 year, and 2 to 5 years annually
- Six-minute walk test: Post-procedure 30 days and 1 year
- Quality of life (QOL) (EuroQOL, short form 12-item health survey [SF-12]): Post-procedure 30 days, 6 months, 1 year, and 2 to 5 years annually

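### By-visit summaries of NYHA, 6-minute walk and QOL have no paired change and no place for deaths, so selective death alone could look like improvement

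*Combined protocol and SAP*

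**What the plan says.** Protocol Section 15.1.2 plans no tests for the secondary endpoints, only descriptive statistics. For 6-minute walk and QOL scores the rule is: "For continuous variables, the number of measurements, mean, standard deviation, median, quartile, minimum, maximum, and 95% CI of the mean will be calculated". NYHA class falls under the next sentence, which gives n and % for categorical variables (with a 95% CI for binary ones). Section 15.1.1.2 assigns the secondary efficacy endpoints to the as-treated (AT) set, that is, subjects in whom the procedure was started.

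The schedule in Section 9.2.2 is long for NYHA: "NYHA classification: Post-procedure 30 days, 6 months, 1 year, and 2 to 5 years annually". QOL follows the same schedule. The 6-minute walk is done only at 30 days and 1 year.

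Four other sections bear on who has a value:
- Section 14.1 lists death as a reason for discontinuation.
- Section 7.3 ends follow-up for subjects without an implanted study valve, although they remain in the AT set once the procedure has started.
- Section 14.3 follows up a missed visit by asking about survival and adverse events only.
- Section 7.1 says that baseline tests are taken for comparison with follow-up values.

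Nothing in the text gives a death category, a fixed denominator, a within-subject change or a missing-value rule for these three measures. Section 15.1.2 leaves further detail to a separate Statistical Analysis Plan, whose text was not available for this review.

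**The concern.** The trial has one arm, so the natural reading of these tables is later visits against baseline, as Section 7.1 intends. The baseline column describes nearly everyone treated. Each later column describes those still alive and assessed. If subjects in poor condition die sooner, later columns look better even when no individual has improved, and marginal summaries cannot separate this from real benefit.

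NYHA, walk distance and QOL are the only functional results in the trial, and Section 1.1.3 asks for efficacy to be confirmed over 5 years. What is at stake is how those results are read. The mortality test against the performance goal does not depend on them.

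**Working it through.** **Source of the mortality inputs.** The 1-year value is the planning assumption in the sample-size text: "With the predicted mortality (true value) at 1 year post-procedure of 20% and PG of 45" per cent, with "one-sided alpha of 0.05 was calculated as 24 subjects". The stated power, "A sample size of 24 subjects will provide 81.1% power by one-sided Fisher's exact test", reproduces as an exact binomial calculation. With 24 subjects the rule is at most 6 deaths, the exact one-sided level is 0.0364, and the power at 20% mortality is 0.8111. The target of 30 matches 24 / (1 − 0.20) = 30, although no drop-out rate is stated.

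For year 5 the protocol gives only survival after surgical valve replacement in Japanese dialysis patients (Section 4.2.1): "at 5 years post-procedure 30% to 60" per cent. The complement is 40% to 70% dead. As a rough cross-check, a constant hazard from 20% at 1 year gives 1 − 0.8^5 = 67.2%, which lies inside that range. Of 30 treated, these rates leave 24 alive at 1 year and 18 to 9 at year 5.

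**NYHA: composition effect with nobody changing class.** Let q be the baseline share in III/IV, m the total mortality and RR the relative risk of death for III/IV against I/II.
- Risk of death in I/II: pL = m / (q·RR + 1 − q). Risk in III/IV: pH = RR·pL.
- Share in III/IV among survivors: q(1 − pH) / (1 − m).

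The value q = 50% is an assumption, taken from the advanced-medical-care column of Table 4-3. RR is also assumed. Worked case, m = 0.20 and RR = 2: pL = 0.20/1.5 = 0.133, pH = 0.267, share = 0.5 × 0.733/0.80 = 45.8%.

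| Dead | RR 1 | RR 1.5 | RR 2 | RR 3 |
|---|---|---|---|---|
| 20% | 50% | 47.5% | 45.8% | 43.75% |
| 40% | 50% | 43.3% | 38.9% | 33.3% |
| 70% | 50% | 26.7% | 11.1% | 0% (pH capped at 1) |

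At 20% dead the fall is 2.5 to 6.25 points for RR 1.5 to 3. With RR = 1 there is none. At the 10.7% mortality seen in advanced medical care (Section 4.3), the same formula gives 48.8% (RR 1.5) to 47.0% (RR 3), a fall of 1.2 to 3.0 points. With 85% in III/IV at baseline (one surgical series in Table 4-3) and RR 2, the shares are 83.3%, 80.4% and 68.9% at 20%, 40% and 70% dead.

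**Effect of counting death.** In the RR 2 case, the share in III/IV or dead is m + (1 − m) × the survivor share: 0.20 + 0.80 × 0.458 = 56.7%; 0.40 + 0.60 × 0.389 = 63.3%; 0.70 + 0.30 × 0.111 = 73.3%. The apparent improvement disappears. A baseline-to-visit shift table would show no subject changing class.

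**Continuous scores, no individual change.** With a hazard ratio for death of 1.5 per SD worse score (assumed), the survivor mean rises 0.09 SD at 20% dead, 0.20 SD at 40% and 0.45 SD at 70%. With a hazard ratio of 2 it rises 0.15, 0.31 and 0.66 SD. With a hazard ratio of 1 it does not move. Only the 20% figures apply to the walk test; all three can apply to QOL.

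**Denominator, a separate matter.** If 90% of survivors are in class I/II (assumed) and 20% have died, 0.90 × 0.80 = 72% of treated subjects are alive in class I/II.

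**The case against.** The strongest reply is that silence is not a rule. Section 15.1.2 lists generic statistics for all variables and defers detail to the separate Statistical Analysis Plan, where denominators and paired change would normally be set out. A reader might infer that the protocol prescribes a survivors-only analysis; it does not say so. That inference comes from which values can exist, and the separate plan could contain a remedy. This part of the objection stands.

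The gap between 90% and 72% is also not bias. It is one result on two denominators, and death is reported at every visit, so a reader could combine them. That stands too. It does not settle the composition effect, because marginal summaries plus a mortality curve cannot recover within-subject change.

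Finally, the endpoints are untested, the shift depends on an assumed link between death and poor status, and it is small at 1 year. All true. These points limit the weight of the finding but do not remove it, since NYHA and QOL are reported annually to 5 years.

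**Conclusion.** The concern holds in a limited form. As written, Section 15.1.2 would let selective death appear as functional improvement, and nothing in the text reviewed prevents it. The size rests on assumed relative risks and an assumed 50% baseline share in NYHA III/IV. It is modest at 1 year (about 2.5 to 6 points at 20% mortality) and zero if death is unrelated to status. It can be large by year 5, for NYHA and QOL only.

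Three stronger readings are not supported:
- That 40% to 70% of this trial's subjects will be dead by year 5. That range comes from surgical series with mean ages below 70; the protocol gives no 5-year projection for this population.
- That year-5 walk results are distorted. None are scheduled.
- That the trial's success claim is affected. It rests on 1-year mortality alone.

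**What to change.** In Section 15.1.2 and the separate Statistical Analysis Plan (Section 15.4 gives the revision route), state that:

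1. each visit table reports the numbers alive, assessed and dead;
2. 6-minute walk and QOL are summarised as paired change from baseline in the same subjects with a 95% CI, and NYHA as a baseline-to-visit shift table;
3. NYHA is also shown over all AT subjects with death as its own category, including a row for alive and in class I/II; a further row for subjects not assessed keeps the total complete;
4. summaries restricted to survivors are labelled as such. This includes the paired changes, which remove the change in composition but still describe only those who lived.

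If the separate plan already contains these rules, a cross-reference is enough. Summaries of walk distance or QOL that rank death worst are optional sensitivity analyses, because that ranking is debatable. Giving death a place is not foreign to this protocol: the glossary definition of device success excludes operative death, and its modified Rankin scale scores death as 6.

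The cost is a few extra table rows and figures that look less favourable. No additional assessments are needed.
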